13.1.3. Reporting of Deaths

All deaths including death due to disease progression occurring through the 30-day follow-up period must be reported as an SAE within 24 hours:

- Death is not an acceptable SAE term. Death is an outcome of an SAE. The primary cause of death should be reported as the SAE term.

When reporting a death in the eCRF, site personnel will be required to identify which of the following best describes the category of death:

- Toxicity caused by study drug.
- Radiologic disease progression.
- Clinical disease progression.
- Other causes.

13.1.4. Disease Progression

How to report events related to nonfatal disease progression:

- Disease progression is not an acceptable AE term. In cases of nonfatal disease progression, the relevant major symptoms, signs, and/or complications that led to the diagnosis of clinical disease progression should be reported as an AE. If the relevant symptoms, signs, and complications meet any of the serious criteria, they should be reported as SAEs. In both cases it should be indicated whether the symptoms, signs, and complications are related to clinical disease progression.

How to report events related to fatal disease progression:

- In cases of death due to clinical disease progression, the relevant major symptoms, signs, and/or complications that led to the diagnosis of clinical disease progression should be reported as SAE terms. Clinical disease progression may only be reported as an SAE term if none of the relevant symptoms or signs support a fatal outcome.

13.1.5. Pregnancy

If a patient becomes pregnant while in the study, the study treatment must be immediately discontinued. Pregnancy information in a female patient should be reported **within 24 hours** from the time the investigator first becomes aware of a pregnancy or its outcome. This should be performed by completing a Pregnancy Form and faxing it to Taiho Pharmacovigilance or designee.

New and/or corrected information regarding the pregnancy obtained after submitting the Pregnancy Form must be submitted by faxing an updated Pregnancy Form to Taiho Pharmacovigilance or designee.

If the outcome of the pregnancy is a stillbirth, congenital anomaly/birth defect, or a serious event in the mother, report as an SAE to Taiho Pharmacovigilance or designee.

13.1.6. Overdose

An overdose with TAS-114 and S-1 for this clinical trial is defined as:

Taking a dose beyond the recommended dose in 1 day or beyond the recommended total dose in each cycle.

An overdose of TAS-114 and/or S-1 must be recorded on the AE and SAE Forms and reported to Taiho Pharmacovigilance, or designee, within 24 hours from the time the investigator first becomes aware of the overdose whether or not it was accidental or intentional, and whether or not the patient developed an AE (even if not fulfilling a seriousness criteria).

There is no known antidote available in case of TAS-114 and/or S-1 overdose. Overdose should be managed aggressively with close monitoring and administration of prophylactic and symptomatic therapies to prevent or correct potential side effects.

An accidental or intentional overdose for concomitant medications should only be reported if it is associated with an AE.

13.1.7. Medication Errors

A medication error for this clinical trial is defined as an accidental, incorrect administration of a medicinal product. The error may be related to the administration of a wrong medication, nature of the medication, route of administration, dosage, or frequency of the treatment (including omission of one or more administrations).

Please refer to the current eCRF Completion Guidelines for the details regarding reporting of medication errors to Taiho Pharmacovigilance or designee.

The following types of medication errors, whether or not they meet the serious criteria, should be reported to Taiho Pharmacovigilance **within 24 hours of first awareness**, utilizing the AE and SAE forms in the eCRF:

- Medication errors with study drug or concomitant medication resulting in an AE
- Medication errors with study drug resulting in an overdose
- Incorrect route of study drug administration
- Administration of the incorrect study drug

Medication errors with the study drug that result in the omission of an administration, an incorrect dose, or the administration of more than the prescribed dose (but does not meet the overdose criteria), will not be reported as an AE, but will be identified through the recording of study drug accountability data in the eCRF.

13.1.8. Breaking the Study Blind

This is an open-label study.

13.2. Laboratory Evaluations

13.2.1. Reporting and Evaluation of Laboratory Test Results

Laboratory tests are to be performed as required per the protocol. All laboratory values that are out of the normal range are to be evaluated for their clinical significance before exposing the patient to the next dose of TAS-114/S-1 or S-1 control.

The laboratory must provide normal reference ranges.

Any laboratory abnormality that has a clinical impact on the patient (eg, results in delay of TAS-114/S-1 or S-1 control dosing, study discontinuation) must be reported as an AE, unless it is considered a supporting laboratory to a clinical diagnosis that is already reported as an AE. Febrile neutropenia must be reported as an AE and is defined as an ANC < 1000/mm³ with a single body temperature of > 38.3°C (101°F) or a sustained temperature of ≥ 38°C (100.4°F) for more than 1 hour. All laboratory data will be analyzed using NCI CTCAE grade criteria (Version 4.03).

13.2.2. Repeat Testing

Evaluation of any clinically significant laboratory test will be repeated, as clinically indicated, until the value returns to the baseline level or clinically stabilizes, or until new anticancer treatment, surgery, or radiotherapy is given.

13.3. Physical Examination and ECOG Performance Status

Physical examinations and performance status evaluations will be performed as described in the Study Procedures section of the protocol. If changes are observed, the investigator will determine whether they meet the definition of an AE. All observations and evaluations will be documented.

13.4. Vital Signs and Body Weight

Vital sign measurements and body weight will be verified and documented. If a clinically significant change is observed, the measurement will be repeated as clinically indicated and evaluated for its clinical relevance and whether it meets the definition of an AE.

14. STATISTICS

This section outlines the statistical methodology to be used to summarize the study results. An SAP will be prepared as a separate document. The SAP will include a more technical and detailed description of the planned statistical summaries and will be finalized prior to closing of the database.

Study Populations

The study populations include safety and efficacy populations.

Safety and Efficacy Populations

All safety and efficacy analyses will be based on patients who received at least 1 dose of TAS-114/S-1 or S-1 control.

14.1. Statistical Analysis

14.1.1. Patient Disposition, Baseline and Treatment Characteristics

14.1.1.1. Patient Disposition

The number of patients in each study population and the reasons for exclusion will be summarized. In addition, patients' status with regard to study treatment and follow-up will also be summarized, along with the reasons for study discontinuation.

14.1.1.2. Patient Baseline Characteristics

Patient disease and baseline characteristics will be summarized using frequency distribution or descriptive statistics as appropriate.

14.1.1.3. Study Treatment

The TAS-114/S-1 or S-1 control administration profile will be summarized with respect to number of cycles taken, the dose intensity, dose modifications, reasons for deviations from the planned regimen, and the reason for discontinuing the study treatment.

14.1.2. Efficacy Analysis

Tumor assessments will be performed as described in [Section 11.12](#), Tumor Assessments/Scans, for patients with solid tumors. The primary endpoint of PFS and secondary endpoints of ORR, DCR, and DR will be investigated based on the independent review of the images by the Core Imaging Laboratory. The investigators or local radiologists will evaluate the imaging studies for tumor response and/or progression. Response assessments will be made based on RECIST guidelines (Version 1.1, 2009) for solid tumors (see [Section 12.1](#), Efficacy Assessment for Solid Tumors).

14.1.2.1. Primary Efficacy Analysis

14.1.2.1.1. Progression Free Survival

PFS is defined as the time from the day of randomization to the start of disease progression or death (any cause), whichever occurs first, based on the blinded radiological review assessment of response. Patients who do not have disease progression or have not died will be censored at the last known time that the patient was progression free.

PFS in the efficacy population will be compared between the 2 treatment groups using the stratified log-rank test with significance level of one-sided 5%. PD events assessed by the central independent review will be used for primary efficacy analysis. The estimate of the hazard ratio and corresponding 90% and 95% confidence interval (CI) will be provided using a Cox proportional hazards (CPH) model including treatment and the 2 stratifications factors in the model. The survival curves will be estimated using the Kaplan-Meier method. The primary analysis for PFS will be conducted after 60 events have been observed based on independent assessment or after all patients have been followed for at least 3 months, whichever is later.

14.1.2.2. Secondary Efficacy Analysis

14.1.2.2.1. Overall Survival

OS is defined as the time from the day of randomization to any cause of death. The estimate of the hazard ratio and corresponding 95% CI will be provided using a univariate CPH model (only treatment effect in the model). The survival curves will be estimated using the Kaplan-Meier method. The unstratified log-rank test will be done for the comparison of treatment effect.

14.1.2.2.2. Overall Response Rate and Disease Control Rate

ORR is defined as the proportion of patients with objective evidence of CR or PR. The evaluation of ORR will be based on investigator assessment and/or central independent review of the images

- Local CT image assessment and collect CT scans for central independent review

At the analysis stage, the best overall response will be assigned for each patient as the best response recorded after initiation of study treatment. If applicable, responses recorded after disease progression or initiation of new anticancer treatment will be excluded.

The assessment of DCR will parallel that of ORR, with DCR defined as the proportion of patients with objective evidence of CR, PR, or SD.

ORR and DCR in the efficacy population will be compared between the 2 treatment groups using Fisher's exact test. The estimates and differences will be presented along with the associated 95% CIs.

14.1.2.2.3. Duration of Response

DR is derived for those patients with objective evidence of PR or CR. DR is defined as the time from the first documentation of response (CR or PR) to the first documentation of objective tumor progression or death due to any cause. Patients who are alive and progression free as of

the analysis cut-off date will be censored at their last evaluable tumor response assessment before initiation of any new anticancer cancer treatment.

Duration of response will be analyzed in the same manner as OS.

14.1.3. Safety

The safety evaluations will focus on the AEs and laboratory assessments. All patients included in the safety population will be evaluated in the safety analysis.

Adverse events will be coded according to the Medical Dictionary for Regulatory Activities (MedDRA) terminology and the severity of the toxicities will be graded according to the NCI CTCAE (Version 4.03) where applicable. Concomitant medications will be coded according to World Health Organization (WHO) Drug Dictionary for Concomitant Medication.

All AEs will be summarized (incidence) and listed by the system organ class, preferred term, toxicity/severity grade, and causal relationship to TAS-114/S-1 or S-1 control. In addition, separate summaries of SAEs and grade 3 or 4 AEs will be presented.

Hematological and chemistry laboratory parameters will be graded according to the NCI CTCAE (Version 4.03) where applicable. The worst severity grade, time to maximum grade 3 or 4 value, and time to resolution (return to baseline grade or below) will be summarized.

CCI

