#### 6.3.5 Laboratory Data

Laboratory assessments include:

- Hematology: red blood cell (RBC) count, hemoglobin, hematocrit, platelets, white blood cell (WBC) count with differential, neutrophils (both segmented and band neutrophils), lymphocytes, monocytes, eosinophils, basophils.
- Serum chemistry: aspartate aminotransferase (AST), alanine aminotransferase (ALT), alkaline phosphatase (ALK), albumin, total bilirubin (direct bilirubin, indirect bilirubin), creatinine, sodium, potassium, calcium, chloride, blood urea nitrogen (BUN) or urea, phosphorus, bicarbonate, glucose, creatine kinase (CK)/creatine phosphokinase [CPK] (creatine kinase MB, creatine kinase MM) .
- Coagulation: international normalized ratio (INR), activated partial thromboplastin time (aPTT)
- Urinalysis: urinary protein (qualitative), urinary glucose (qualitative), and urine specific gravity density.

All laboratory data will be stored in the database with the units in which they are originally reported. Laboratory data in summary tables and subject data listings will be presented in the International System of Units (SI units; *Système International d'Unités*). Laboratory data not reported in SI units will be converted to SI units before further processing or data analysis.

Baseline value is the subject's last observation prior to the initiation of study drug (including Cycle 1 Day 1).

Laboratory tests will be graded using NCI-CTCAE v4.03 toxicity grading (see [Appendix 1](#)).

**Time to maximum/worst grade 3 or 4 value** (in days) is defined as the time from the date of first study treatment to the earliest date of maximum or minimum (nadir) laboratory parameter value with Grade 3 or above: (date of maximum/worst grade 3 or above – date of first study treatment + 1). If toxicity grade is defined for abnormal high/increase in NCI-CTCAE grading criteria, maximum is used. Otherwise, minimum (nadir) is used.

If there is no grade 3 or 4 laboratory value, the time to worst grade 3 or 4 value analysis will be censored at their last available laboratory assessment before the initiation of any new anti-cancer treatment, if applicable.

**Time to resolution** (in days) is defined as the time from the date of the worst grade 3 or 4 value to the earliest date of the laboratory parameter value return to baseline grade or below with an improvement of at

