least one grade for the same type of abnormality (high/low): (date of return to baseline grade or below – date of worst grade 3 or above +1).

In case the laboratory value does not return to baseline grade or below, the time to resolution analysis will be censored at their last available laboratory assessment before the initiation of any new anti-cancer treatment, if applicable.

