### **7.1.5 Laboratory Data**

Hematology, serum chemistry, and coagulation results will be summarized by toxicity grade (using NCI-CTCAE v4.03 toxicity grading – see [Appendix 1](#) at baseline and post-baseline measurements that worsened by at least one grade. Local laboratory ranges will be used for grading. In the event a range is not available a standard set of lab ranges as detailed in [Appendix 3](#) will be utilized and flagged in the database.

The worst change from baseline in toxicity grade for selected laboratory parameters will also be presented in shift tables: in each treatment arm, the patient's baseline grade will be cross-tabulated by the patient's maximum post-baseline grade during the treatment.

Time to maximum/worst grade 3 or 4 value and time to resolution will be summarized for all quantitative laboratory parameters if toxicity grade is defined in NCI-CTCAE v4.03. The Hematology parameters will include Hemoglobin, Hematocrit, RBC, WBC, ANC, Thrombocytopenia, and Platelets, and the Chemistry

parameters will include AST, ALT, Total Bilirubin, and Alkaline Phosphatase. Count of the events and the censored, minimum and maximum of the event time will be presented by treatment group. Meanwhile, median time to worst grade 3 or 4 value and time to resolution for each group being compared will be estimated using the Kaplan-Meier method, along with the corresponding 95% CI.

The qualitative urinalysis results will be summarized by visit and treatment groups. A shift table for qualitative urinalysis results from baseline to worst past-baseline will also be presented.

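### Time to resolution of Grade 3/4 laboratory values censors patients who die unrecovered, so the Kaplan-Meier estimate somewhat overstates recovery (minor)

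*Protocol*

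**What the plan says.** Protocol 14.1.3 lists the summary without a method: "time to resolution (return to baseline grade or below) will be summarized". The method is in the SAP.

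- **Clock.** SAP 6.3.5: the interval "is defined as the time from the date of the worst grade 3 or 4 value to the earliest date of the" laboratory value's return to baseline grade or below, with at least one grade of improvement. It is computed as "date of return to baseline grade or below – date of worst grade 3 or above +1".
- **Censoring.** The rule opens "In case the laboratory value does not return to baseline grade or below" and continues that "the time to resolution analysis will be censored at their last available laboratory assessment before the initiation of any new anti-cancer treatment", where applicable. It covers every non-return, whatever the reason. Death has no rule of its own.
- **Estimator.** SAP 7.1.5: median "time to resolution for each group being compared will be estimated using the Kaplan-Meier method", with a 95% CI.
- **Counts.** SAP 7.1.5: "Count of the events and the censored, minimum and maximum of the event time will be presented by treatment group". Reasons for censoring are not requested.

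Protocol 13.2.2 has clinically significant tests repeated, as clinically indicated, "until the value returns to the baseline level or clinically stabilizes, or until new anticancer treatment, surgery, or radiotherapy is given". The visible text of the SAP gives no competing-risk method for this endpoint.

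**The concern.** Kaplan-Meier assumes that a censored patient keeps the same future chance of resolving as the patients still under observation. After death that chance is zero. After a switch of therapy the patient may still recover, but protocol-driven repeat testing has ended, so any recovery goes unseen. In both cases the censoring is tied to the outcome.

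The extreme case is a patient whose worst value is also the last sample. That patient is censored on day 1 and has no influence on the shape of the curve.

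Safety and tolerability is a stated secondary objective (Protocol 7.2), and how fast severe laboratory toxicity reverses is part of judging an add-on drug. If more patients in one arm die or switch unrecovered, the Kaplan-Meier medians show less of that difference than they should.

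**Working it through.** The documents state no figure for time to resolution, so there is nothing to reproduce. The check compares one minus Kaplan-Meier with the share of all Grade 3/4 patients who resolve.

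**Inputs**
- From the documents: median PFS 2.2 months (S-1) and 4.2 months (TAS-114/S-1), Protocol 14.2; median survival of about 8 to 10 months, Protocol 6.1; 30.4375 days per month, SAP 6.2.1.
- Assumed: recovery is exponential with a median of 8 days (14 days as a sensitivity case). u is the share who die or start new therapy unrecovered, and 10% to 30% is examined.

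**Step 1. A share u from the design figures.** Take constant, independent hazards: r for recovery, c for the competing event. Then u = c/(r+c) = (recovery median)/(recovery median + competing median). Suppose, generously, that every PFS event is at once a death or a switch.
- S-1: 2.2 × 30.4375 = 67.0 days; u = 8/(8 + 67.0) = 10.7%.
- TAS-114/S-1: 4.2 × 30.4375 = 127.8 days; u = 8/(8 + 127.8) = 5.9%.
- Death alone at 8 to 10 months (243.5 to 304.4 days): u = 8/251.5 = 3.2% to 8/312.4 = 2.6%.

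**Step 2. Shift in the median, constant hazards.** The cumulative incidence of resolution is (1−u)(1−exp(−(r+c)t)), with r = ln 2/8 = 0.0866 per day and r+c = r/(1−u). Its median is −ln(1−0.5/(1−u))/(r+c). The Kaplan-Meier median stays at 8.0 days.

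| u | Cumulative-incidence median (days) | Shift (days) |
|---|---|---|
| 5.9% | 8.2 | 0.2 |
| 10.7% | 8.5 | 0.5 |
| 20% | 9.1 | 1.1 |
| 30% | 10.1 | 2.1 |

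Sensitivity: with a 14-day recovery median the same formula gives 14.7, 15.8 and 17.7 days at u = 10%, 20% and 30%. The implied share also rises, to 14/(14 + 67.0) = 17% and 14/(14 + 127.8) = 10%.

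**Step 3. Dependence on the last sample.** Now let a share u never resolve before death or new therapy, and let the rest recover with a median of 8 days. Times are rounded up to whole days plus the SAP's extra day, so recovery by day 21 among recoverers is 1 − 2^(−20/8) = 82.3%. The share of all patients resolved is (1−u) × 82.3%. The Kaplan-Meier columns are large-sample values, with resolutions counted before censorings on the same day.

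| Resolved by day 21 | u = 10% | u = 20% | u = 30% |
|---|---|---|---|
| All patients | 74% | 66% | 58% |
| Kaplan-Meier, last sample is the worst value | 82% | 82% | 82% |
| Kaplan-Meier, last samples spread over days 1–14 | 81% | 79% | 77% |
| Kaplan-Meier, last samples spread over days 1–30 | 77% | 72% | 65% |
| Kaplan-Meier, all last samples on day 30 | 74% | 66% | 58% |

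The all-patient medians are 11, 13 and 16 days. With the worst value last, the Kaplan-Meier median is 9 days throughout, a shortfall of 2, 4 and 7 days.

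**Reading.** Kaplan-Meier is never below the all-patient figure, so the error runs one way. For arms with u = 10% and 30%, the real gap of about 16 points (74% vs 58%) appears as 4 points under the 14-day spread (81% vs 77%) and 12 under the 30-day spread (77% vs 65%).

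**The case against.** **The censored counts are already planned.** SAP 7.1.5 tabulates events and censored by arm, so shares of 10% and 30% would be visible in the same output. Fatal adverse events, events leading to discontinuation, causes of death, grade shift tables and new anti-cancer treatments are also reported (SAP 7.1.3 to 7.1.5 and 7.1.9). This stands. What is missing is the reason for censoring, which those separate tables do not link to the laboratory event.

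**The schedule works against the extreme case.** Samples are due on Days 8 and 15 of Cycle 1, at later cycle visits, at End of Treatment and at the 30-day visit (Protocol 11.7.1, 11.7.2). That visit should precede new therapy (Protocol 11.13). This also stands. A reader might infer from the first Kaplan-Meier row in Step 3 that the analysis can make two unequal arms look identical. That needs every non-recoverer's worst value to be the last sample, and the planned visits do not support it.

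**New therapy is not failure to recover.** A reader might also infer that everyone censored never recovered. That is certain only for patients who die. Those who switch may resolve unobserved, so counting the switch as a competing event is a choice of estimand and should be labelled as one.

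**The consequence is small.** No test is planned on this endpoint. Each parameter uses only the Grade 3/4 subset of about 62 patients per arm (124/2), so a shift of half a day could be lost in the confidence interval. This is fair, and it limits the severity. It does not justify an estimator that treats the dead as able to recover.

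**Conclusion.** The concern holds as a minor point. Censoring patients who die unrecovered makes resolution look more frequent and faster, and nothing in the visible SAP corrects it.

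The size cannot be computed from the documents. Under an assumed 8-day recovery median and constant, independent hazards, the design PFS implies a share of about 6% to 11% and moves the median by half a day or less. If the share were 20% to 30%, the shift would be one to two days under constant hazards and four to seven days if the worst value were also the last sample. Patients with severe toxicity may fare worse than the average that the PFS figures describe, so the lower range is not guaranteed.

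The bias weakens a difference between arms without fully hiding it. Its direction between arms is not fixed: the design PFS figures give the larger share to S-1, while added toxicity would give it to the combination. The PFS analysis is not touched.

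**What to change.** In SAP 6.3.5 and 7.1.5:

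1. Estimate time to resolution as a cumulative incidence (Aalen-Johansen) by arm, with death before resolution as a competing event.
2. Treat start of new anticancer therapy before resolution as a second competing event. Describe the estimand as resolution before new therapy, and do not describe these patients as never having recovered.
3. Split the planned censored count by arm into died unresolved, started new therapy unresolved, and unresolved at last sample.
4. Keep the Kaplan-Meier median as supportive.

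No new visits or data are needed: deaths and new treatments are already collected (SAP 6.3.4, 6.3.12). The cost is a few lines of SAP text and some programming. The small downside is that medians become somewhat longer or may not be reached.
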